Study overview. Participants will be 250 community smokers, currently interested in quitting smoking, who will be randomly assigned (stratified by gender) to receive either ABM or sham training. Smokers in both groups will attend three laboratory sessions (Figure 2). The first lab session will establish each smoker's baseline smoking behavior and AB towards smoking picture and word cues by assessing reaction time (RT) and event-related potential (ERP) electroencephalography to modified dot-probe (MDP), Stroop color-word naming tasks and a passive picture viewing task. After the first lab session, participants will complete 13 days of daily in-home training (ABM or sham) and AB assessments that will be administered through a provided smartphone, with compliance and accuracy rewarded monetarily. The second lab session will occur the day after the final day of in-home training and will involve the same assessments as the first session, to gauge the short-term impact of ABM on AB and smoking behavior. At the end of the second lab session, participants will have a 30-minute counseling session with a smoking cessation counselor and be given the first half of an 8-week supply of NRT. The participants will be instructed to quit the next day, and will have 3 biweekly phone counseling sessions while on NRT. After participants complete one biweekly phone counseling session, they will be mailed the remainder of their 8-week supply of NRT. Participants will be given a window of seven days after the scheduled date of their second lab session to complete the session. The final lab session, which will occur 8 weeks after the second session, will measure the longer-term impact of training on smoking behavior and AB. Participants will be given a window of fourteen days after the scheduled date of their final lab session to complete the session. Out of window visits will be noted in the progress notes but will not be considered a protocol deviation. Visit 3 has a window with an ending period of whenever final abstinence data is collected or the trial ends, whichever is sooner. A study staff member will make attempts to contact participants who miss Visit 3 until the end of the study or until the participant requests no further efforts be made to contact them. For those who miss Visit 3, a study staff member will call them to invite them to come in as originally planned so that abstinence (e.g., TLFB assessment since last contact, CO, urine cotinine, and anabasine), and lab data can be collected. If participants are unable to attend Visit 3, staff will ask participants to complete TLFB over the telephone to record CPD since last visit. Staff also will offer to send participants' questionnaires via email. If smoking abstinence is reported, staff will invite participants to come in or will offer to send them a NicAlert or comparable urine cotinine test to biochemically verify abstinence. Participants will be asked to send a picture of the cotinine test to research staff via text message, email, or postal mail.

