Baseline laboratory session: Final eligibility. Participants will be instructed to smoke ad lib prior to their baseline lab session. At the baseline, which will occur within 30 days of the telephone screen, participants will have their smoking status assessed, as a final determinant of eligibility, using expired CO or the NicAlert strip. To determine eligibility with the Major Depression and suicidality criteria, participants will complete the Patient Health Questionnaire-9 (PHQ-9), a reliable and valid self-administered diagnostic instrument that assesses depression severity and risk for suicide [62,63]. Additionally, the subject will be assessed for interest in providing a genetic sample according to procedures described in our IRB-approved genetic banking protocol (Protocol # Lab 09-0099). Any individual who is deemed ineligible for study participation due to the PHQ-9 will be assessed by a master's level counselor and will be given referral recommendations for local psychiatric resources (see "Project SmartMod Mental Health Procedures" in the Appendix, for details). Urine will be collected and tested to evaluate eligibility on the drug use and pregnancy criteria, and participants will be considered ineligible if they are pregnant or have a positive toxicology screen for any of the following drugs: cocaine, opiates, methadone, benzodiazepines, barbiturates, amphetamines, methamphetamines, PCP, or THC. Final eligibility will be determined by the PI, [name], a licensed and credentialed psychologist, and his designated study staff members.

Laboratory sessions: Smoking behavior assessment. Prior to each of the 3 lab sessions, participants may be sent a link to complete the visit questionnaires via email. At each of the 3 lab sessions, participants will provide an expired CO sample, a urine sample to measure cotinine (a tobacco metabolite that measures nicotine exposure) and anabasine (a tobacco metabolite that will allow us to distinguish NRT use from smoking [64]), and complete TLFB [65] to record CPD for the prior seven days at visit 1 and CPD since last visit for visits 2, 3 and each of the telephone counseling sessions. Next, if not previously completed, participants will complete a computerized battery of questionnaires related to smoking behavior. Nicotine

[figure not shown]

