Smoking cessation: NRT and counseling. Smokers entering this study will be told that formal smoking cessation treatment will begin the day following Laboratory Session 2. At the end Laboratory Session 2, following the questionnaires and AB assessment, a master's level counselor will meet with the participant. The counselor will provide the participant with the first 4 weeks of an 8-week supply of NRT (NicoDerm CQ; GlaxoSmithKline, Research Triangle Park, NC), instruct the participant on the use of NRT, provide a smoking cessation treatment manual based on PHS guidelines (see the Appendix), and prepare the participant to quit smoking during a 30-minute counseling session. The participant will be educated and provided literature on the use and risks of nicotine patch use, and will be asked to begin using NRT and quit smoking the following day. Participants who complete at least one counseling call in this study will receive 8 weeks of NRT, consisting of 4 weeks of 21-mg patches, 2 weeks of 14-mg patches, and 2 weeks of 7-mg patches. The NRT treatment duration was chosen because meta-analysis suggests that there is little benefit of using NRT beyond 8 weeks [113]. During the 8 weeks of NRT use, participants will receive three biweekly 15-min counseling calls from the counselor (study days 29, 43, & 57; see **Figure 2**, above). Participants will be given a window of three days before and/or after the scheduled date of their phone counseling sessions to complete the session. During these phone sessions, the counselor will assess participants for medication changes, and patch and tobacco usage. At least two call attempts will be made during the course of the day however before the call will be considered missed. Missed phone sessions will be recorded in the study database but will not be logged as protocol deviations because they are expected in smoking cessation trials. After the last day of NRT use (study day 72), participants will return for their final laboratory session. Adverse events will be assessed throughout the study, and participants may choose to reduce or stop the NRT dosage in the unlikely event of dangerous or distressing adverse events. Our procedures for dispensing NRT, evaluating study compliance, and assessing adverse events follow standard FDA and clinical practice guidelines [114] and are well established in our research programs (e.g., [115,116]). Occasionally, research subjects may fail to utilize the NRT patch as instructed. In such cases, subjects will be instructed to mark the patch as missed in their smoking diaries and return the missed patch to the study team. Returned medications patches will be logged, stored in a locked file cabinet maintained by the study team, and will be destroyed per institutional guidelines. Missed patches and missed returns will not be logged as protocol deviations because they are expected in smoking cessation trials. In our previous trials about 75% of all participants take at least 80% of their intended patch use. Only adverse events related to use of the nicotine patch will be reported. The NRT and counseling component will be overseen by co-I [name], who has over 25 years of experience designing and conducting smoking cessation trials.

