
Statistical Approach & Expected Outcomes

Aim 1. Identify the impact of in-home ABM on AB. We will evaluate this aim using 2 (group: ABM vs. sham) X 3 (session: baseline, 1-day post-training, and 8-weeks post-training) linear mixed model using RT difference scores (neutral-cigarette) as the dependent measures and subject as the random effect. We will conduct separate analyses on the dependent measures (within-modality: MDP RT difference scores; between-modality: Stroop RT difference scores) collected at baseline, 1-day post-training, and 8-weeks post-training. We predict that post-training AB scores, calculated from RT, will decrease from baseline for those in the ABM training, but not in the sham training condition, indicating a reduction in AB to smoking cues.

Aim 2. Identify the impact of in-home ABM on smoking behavior. We will evaluate this aim using two types of models. For the continuous (i.e., normally distributed) measures of smoking behavior, we will conduct mixed between-within repeated measures ANOVA using the same predictors and covariates as are described in Aim 1. Separate analyses will be run for each of the continuous dependent measures, including mean CPD over the past 7 days, expired CO, cotinine, FTND, and WSWS Craving. We expect that ABM training, compared to sham training, will decrease measures of smoking exposure (CPD, expired CO, cotinine), levels of dependence (FTND), and levels of craving (WSWS Craving) at the 1-day and 8-weeks post-training sessions. For the categorical variable of 8-weeks post-NRT abstinence, we will conduct a chi-square test of independence on the 2 (abstinent vs. nonabstinent) x 2 (ABM vs. sham training) table. We expect that ABM training, compared to sham training, will result in a higher rate of abstinence.

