Power analysis. To demonstrate that this proposal has adequate sample size to detect meaningful amplitude changes in the continuous measures taken at the post-training laboratory sessions (Specific Aims 1 & 2), we conducted a power analysis using the G*Power program (v3.1.2; Heinrich Heine University, Düsseldorf, Germany). We calculated power to ensure that we could detect a significant 2-way (ABM intervention by time) ANOVA interaction for any of our continuous measures, as assessed at the baseline, 1-day post-training, and 8-weeks post-training sessions. If we assume a conservative Bonferroni-corrected Type I error rate of $\alpha=0.01$, 250 participants, moderately correlated within-subject observations ($r=0.5$), and a conservative nonsphericity correction ($\varepsilon=0.75$) we have 80% power to detect differences corresponding to a Cohen's f of 0.11 or larger for the 2-way interaction. Even if we were to experience an unlikely 30% attrition rate, we would have power to detect a Cohen's f of 0.13 or larger. According to Cohen [117], a Cohen's f of 0.10, 0.25, and 0.40 correspond to a small, medium, and large effect size, respectively, meaning that we have the power to detect a small effect size or greater on our continuous measures. To demonstrate that we would have adequate power to detect likely AB differences for Aim 1, we searched the literature for studies with a similar design to ours. Given that no previous study has evaluated the impact of multi-session ABM on AB in

smokers, we decided to estimate a likely effect size from the one alcohol study that used the MDP task for both multi-session ABM and the AB assessments [2]. We estimated a Cohen's *f* value for this study by taking the square root of the *F* ratio multiplied by the ratio of the degrees of freedom [117]. From this formula, we estimated a Cohen's *f* of 0.64, based on the reported *F* value for the significant ABM training group (ABM, sham) main effect, $F(1,23)=9.4$, $p<.01$. This Cohen's *f* value corresponds to a large effect size and is well within the range for which we have sufficient power to detect. We recognize that this alcohol study does not provide an ideal comparison for the effects sizes we will likely obtain, but it does suggest that ABM produces large effects on AB, effects which should be well within the power requirements of our study to detect.

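### Cigarette counts from the three counselling calls enter no stated analysis, so a participant with no Visit 3 CPD by visit or by telephone gives the Aim 2 CPD model no post-quit information

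*Combined protocol and SAP*

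**What the plan says.** Statistical Approach & Expected Outcomes, Aim 2, specifies a "mixed between-within repeated measures ANOVA using the same predictors and covariates as are described in Aim 1", run separately for "each of the continuous dependent measures, including mean CPD over the past 7 days" and the other continuous measures. Aim 1 defines the time factor as "session: baseline, 1-day post-training, and 8-weeks post-training". The Power analysis names the same three sessions.

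Laboratory sessions: Smoking behavior assessment collects TLFB counts of "CPD since last visit for visits 2, 3 and each of the telephone counseling sessions". Smoking cessation: NRT and counseling schedules "three biweekly 15-min counseling calls from the counselor (study days 29, 43, & 57"). On quitting, the Study overview says: "The participants will be instructed to quit the next day", that is, the day after Visit 2.

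The Study overview also has a fallback: "If participants are unable to attend Visit 3, staff will ask participants to complete TLFB over the telephone to record CPD since last visit". Contact attempts continue until the study ends or the participant asks for them to stop. The Participants section pays for a telephone Visit 3 made up of TLFB and questionnaires. For abstinence, the Power analysis counts missing participants as smoking. No missing-data rule is given for CPD.

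**The concern.** Aim 2 asks about smoking after eight weeks of NRT. In the CPD model that rests on a single post-quit reading. When the reading is absent, the model can predict the participant's post-quit smoking only from how much they smoked before trying to quit. Up to three post-quit readings from the same instrument may already be in the database.

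Two things are at stake. One is precision, because post-quit readings are likely to predict Visit 3 CPD better than pre-quit ones do. The other is the missing-at-random assumption. It is easier to defend when it conditions on smoking after the quit day, because relapse plausibly affects both later smoking and willingness to return. The documents give no figure for either link.

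**Working it through.** **1. The plan's own figures.** The Power analysis uses alpha 0.01, within-subject correlation r = 0.5, nonsphericity ε = 0.75 and k = 2 groups. I took m = 3 sessions and the noncentral F with λ = f²·N·m·ε/(1 − r), df1 = (k − 1)(m − 1)ε = 1.5 and df2 = (N − k)(m − 1)ε.
- N = 250 (df2 = 372): 80% power at f = 0.108, stated as 0.11.
- N = 0.70 × 250 = 175 (df2 = 259.5): 80% power at f = 0.129, stated as 0.13.

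Both reproduce. With m = 6 the values would be 0.086 and 0.103, so the power calculation also leaves out the calls.

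**2. Which CPD readings exist (Figure 2 and the counselling section).**

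| Day | Event | Relative to quit (day 16) | In the Aim 2 CPD model |
|---|---|---|---|
| 1 | Visit 1 | before | yes |
| 15 | Visit 2 | before | yes |
| 29, 43, 57 | calls | after | no |
| 72 | Visit 3, or telephone TLFB | after | yes in person; not stated for telephone |

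The Exploratory analyses use smartphone CPD, which comes from the pre-quit training period, and CPD at each session as a covariate. Neither makes call CPD an outcome.

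**3. Formula.** Let d be the share with no Visit 3 CPD by either route and q the share of those reached on all three calls. Let A be the share of Visit 3 variance explained by Visits 1 and 2, and B the share once the calls are added. Assume a likelihood fit, missing at random, the same pattern in both arms, and all calls completed by those who have Visit 3 CPD. The variance of the Visit 3 arm difference, relative to complete data, is:
- three sessions: (1 − A)/(1 − d) + A
- with calls: (1 − B)/(1 − d) + (B − A)/(1 − d + dq) + A

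**4. Central case.** All correlations here are assumptions: pre-to-post 0.4; adjacent post-quit readings 0.8, multiplied by 0.9 for each further step; Visit 1 to Visit 2 0.7. Then A = 2(0.4²)/(1 + 0.7) = 0.188, and B = 0.664 from the correlation matrix. With d = 0.30 and q = 0.50:
- three sessions: 0.812/0.70 + 0.188 = 1.348
- with calls: 0.336/0.70 + 0.476/0.85 + 0.188 = 1.228
- 1.228/1.348 = 0.911, so variance is 8.9% lower. √0.911 = 0.954, so the interval is about 4.6% narrower.

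**5. Range.** Pre-to-post correlation 0.3-0.5, post-quit correlation 0.7-0.9, the rest as in step 4. The smallest gain is at 0.5/0.7 (A = 0.294, B = 0.552) and the largest at 0.3/0.9 (A = 0.106, B = 0.811).

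| Lacking Visit 3 CPD | Reached on all calls | Variance reduction |
|---|---|---|
| 30% | half | 5-13% |
| 30% | 80% | 7-19% |
| 10% | half | 1-4% |
| 0% | n/a | none |

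**6. A less favourable assumption.** If the plan's 0.5 held for every pair of readings, A = 2(0.25)/1.5 = 0.333 and B = 5(0.25)/3 = 0.417. With d = 0.30 and q = 0.50 the variances are 0.667/0.70 + 0.333 = 1.286 and 0.583/0.70 + 0.083/0.85 + 0.333 = 1.265, a fall of only 1.6%. The gain depends on post-quit readings correlating more strongly with each other than with pre-quit readings.

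**The case against.** A reader might infer that anyone who misses Visit 3 contributes nothing after the quit day. The documents do not support that. The telephone TLFB covers the whole period since the last visit, is paid for as a Visit 3, and is pursued with no fixed end date. The affected group is therefore smaller than the group missing the visit.

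It may be smaller still. The 30% scenario is introduced with "Even if we were to experience an unlikely 30% attrition rate" and is not defined as having no Visit 3 CPD. Missed calls are expected by the protocol, and people who cannot be reached at the end may also have missed the calls. The documents support neither 50% nor 80% reached.

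The plan also names no Visit 3 contrast as its test. It plans and powers a three-session interaction, so replacing that with a Visit 3 comparison would change the analysis rather than improve it. Leaving out auxiliary data is not in itself an error.

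All of this stands, and it limits the point without removing it. The fallback cannot help those who are unreachable or refuse contact. The plan does not say that the telephone TLFB supplies Visit 3 CPD. With an open-ended window, a late TLFB may rest on long recall, whereas calls are due within three days of schedule.

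**Conclusion.** The point holds as a cheap improvement. Call CPD is collected and enters no stated analysis, and participants with no Visit 3 CPD by either route give the model no post-quit information even where call readings exist. The size is modest and rests on assumed correlations, missingness and call reach: the gains in step 5, or less if the correlations resemble step 6. They apply to the arm difference at Visit 3. The baseline-to-day-15 part of the interaction involves no post-quit outcome, so the same percentages should not be read across to the interaction test.

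Two further inferences go too far. Bias in the Visit 3 result is not demonstrated; only the plausibility of missing-at-random is weakened. Nor do the documents say that the Aim 2 ANOVA discards incomplete cases. They leave the fitting method open. If it did discard them, these participants' pre-quit data would be lost too.

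**What to change.** Amend the Aim 2 text for CPD before unblinded data are seen:
- Fit a linear mixed model by likelihood with unstructured covariance, not a complete-case repeated-measures ANOVA. Under a complete-case fit, adding the calls would lose everyone who missed one.
- State that the telephone TLFB supplies Visit 3 CPD where the visit is missed, and which seven days it refers to.
- Include the 7-day mean CPD before each call, either as three extra repeated outcomes or as auxiliary variables in multiple imputation. This needs day-level TLFB entries. Where Visit 2 ran late, check that the seven days fall after the actual quit day.
- Keep the planned group-by-session test over baseline, 1-day and 8-weeks post-training, computed as contrasts within the larger model, so the target quantity is unchanged.
- State how CPD that is still missing is handled.

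No new data collection is needed. The cost is plan text and a little more analysis work. One limitation is that call CPD is self-reported by telephone, as is the Visit 3 fallback.

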AB to drug cues has also been associated with treatment outcome. Among the substance dependent, AB has been associated with treatment compliance [38] and treatment outcome [24–28]. AB, in the form of a smoking Stroop task given on the first day of quitting, was found in one study to be a better predictor of smoking cessation outcome than traditional measures of dependence [28]. Pre-treatment AB to a heroin Stroop task was found to predict 3-months post-treatment relapse status in heroin users attending an inpatient treatment center [27]. In a sample of alcoholics undergoing in-patient treatment, patients who later relapsed after discharge were found to produce increased AB on an alcohol Stroop task given during day 1 and week 4 of treatment, while non-relapsers and controls showed a decrease in AB during that time period [25].

ABM reduces AB to drug-related cues. The theoretical and empirical support for the association between AB and substance use has led many to pursue research into directly altering AB using ABM. ABM for substance abuse developed out of interventions designed to reduce AB in individuals with anxiety, given that a hallmark of anxiety disorders is an AB towards threat-related stimuli [39–41]. The majority of ABM interventions involve a modified visual probe task [42]. The classic visual probe task, used to assess AB, is a measure of visual attention where a pair of photographs, one bias-related (i.e., drug-related) and one neutral, are briefly presented simultaneously on a screen. After both pictures are removed from the screen, a small visual probe is presented in the former location of one of the pictures, with participants instructed to respond to the probe as quickly as possible with a button press. Each picture is probed an equal number of times. Drug dependent participants consistently respond faster to probes occurring in the place of drug-related pictures compared to neutral pictures, including smokers [43], heavy drinkers [44], and the opiate dependent [16], suggesting that drug-related stimuli capture attention in those with drug problems. In the modified visual probe task, used to deliver ABM interventions, the majority or all of the probes replace neutral pictures. This task trains participants to attend to neutral pictures and away from drug-related pictures.

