To demonstrate that this proposal has adequate sample size to detect likely changes in abstinence after 8 weeks of NRT (Aim 2), we conducted a power analysis using G*Power to calculate effect size *w*, the square root of the standardized chi-square statistic [117]. Given a total sample size of 250 (missing participants will be assumed to be smoking), 1 degree of freedom, and a Type I error rate of $\alpha = 0.05$, we have 80% power to detect differences corresponding to an effect size *w* of 0.177 or larger, which means that we will have enough power to detect a difference in abstinence rates of 12.6% or higher between training groups. To estimate likely abstinence rates, we turned to the ABM and alcohol literature, because there are no published ABM and smoking studies that report abstinence outcome. In a study comparing ABM to sham treatment in 214 alcoholics, Wiers and colleagues [3] reported that 54% of those in the ABM group, and 41% in the control group, were abstinent at 1-year follow-up, a difference of 13%. Given that between-group substance-dependence treatment differences are often greatest at the end of treatment, and narrow by 1-year follow-up, we believe that we will have adequate power to detect likely differences in abstinence rates.

Potential Problems & Alternative Strategies

Participant recruitment. We expect to have no difficulty recruiting the needed number of participants. In the past 5 years, for example, our team has recruited more than 800 community volunteers for our various smoking research studies. We have had considerable success enrolling participants into studies involving RT and EEG/ERP recordings and our procedures allow us to collect highly reliable data.

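### Abstinence is tested by a valid but unadjusted chi-square with no effect estimate; pre-specifying a model adjusted for baseline variables would add a little precision at almost no cost

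*Combined protocol and SAP*

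**What the plan says.** **Test.** Under Statistical Approach & Expected Outcomes, Aim 2, the plan states for abstinence: "we will conduct a chi-square test of independence on the 2 (abstinent vs. nonabstinent) x 2 (ABM vs. sham training) table". It names no risk difference, odds ratio or confidence interval for this outcome.

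**Sizing.** The abstinence part of the Power analysis reads "Given a total sample size of 250 (missing participants will be assumed to be smoking), 1 degree of freedom", at a type I error rate of 0.05. It continues "we have 80% power to detect differences corresponding to an effect size *w* of 0.177 or larger", which it translates into "enough power to detect a difference in abstinence rates of 12.6% or higher between training groups". As a guide to likely rates it uses an alcohol study that "reported that 54% of those in the ABM group, and 41% in the control group, were abstinent at 1-year follow-up".

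**Baseline data.** Section D, Laboratory sessions: Smoking behavior assessment, has every participant complete a timeline follow-back "to record CPD for the prior seven days at visit 1", and the FTND is part of the questionnaire battery at the laboratory sessions. The first session precedes training. The Study overview says participants are "randomly assigned (stratified by gender) to receive either ABM or sham training".

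**Adjusted versions.** Exploratory analyses plans to re-examine the Aim 1 and 2 models with covariates. The list holds baseline dependence (written there as FTCD), sex, CPD at each session, sessions completed and training accuracy. Item 2 of that section also looks at whether baseline FTND, CPD and other traits predict response to training.

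**The concern.** In a randomised comparison of a binary outcome, adjusting for baseline variables that predict the outcome keeps the type I error and narrows the interval around the treatment effect. Here such variables are already collected, and counting missing participants as smokers gives all 250 an outcome, so adjustment needs no further data. The chi-square uses none of them. On its own it also returns a p-value without saying how large the effect is or how precisely it is known.

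The exploratory covariate set does not fill this gap. A chi-square cannot carry covariates, and no logistic or other binary model is named. Sessions completed, accuracy and CPD at later sessions are all measured after randomisation. CPD at the final session nearly determines abstinence, so conditioning on it would remove most of the effect being estimated. At stake are some avoidable imprecision and the lack of a pre-specified, interpretable adjusted estimate.

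**Working it through.** **1. The plan's own figure.** Inputs from the Power analysis: N = 250, α = 0.05, 1 df, w = 0.177. The noncentrality is N·w² = 250 × 0.177² = 7.83. Power from the noncentral chi-square is 79.9%, and the w that gives exactly 80% is 0.1772. The stated figure reproduces.

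**2. The rates behind 12.6 points.** With equal arms (assumed, 125 each; the ratio is not stated), d = 2·w·√[p̄(1−p̄)]. Setting d = 0.126 and w = 0.177 gives p̄(1−p̄) = (0.126/0.354)² = 0.127, so p̄ ≈ 0.149. The rates are 0.149 ± 0.063, or about 8.6% vs 21.2%.

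**3. The plan's reference rates.** For 41% vs 54%, p̄ = 0.475 and w = 0.13/(2 × 0.4994) = 0.130. The noncentrality is 250 × 0.130² ≈ 4.2 and power is about 54%.

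**4. Gain from adjustment, by formula.** If the covariates explain a share R² of outcome variance, effective N = 250/(1−R²). R² is an assumption.

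| R² | Effective N | Power at w = 0.177 | Detectable difference at p̄ = 0.149 | Power at 41% vs 54% |
|---|---|---|---|---|
| 0 | 250.0 | 79.9% | 12.6 points | 53.9% |
| 0.02 | 255.1 | 80.7% | 12.5 points | 54.8% |
| 0.05 | 263.2 | 81.9% | 12.3 points | 56.1% |
| 0.10 | 277.8 | 83.9% | 12.0 points | 58.3% |

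**5. Gain from adjustment, by simulation.** 125 per arm, one baseline score, chi-square against a standardised risk difference from logistic regression. The slope is the log-odds per SD of the score, also an assumption. The variance ratio is unadjusted over adjusted. There were 6,000 trials per cell at 8.6% vs 21.2% and 3,000 at 41% vs 54%; the slope-0 rows used 3,000.

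| Rates | Slope | Chi-square | Adjusted | Variance ratio |
|---|---|---|---|---|
| 8.6% vs 21.2% | 0 | 81.3% | 82.0% | about 1 |
| | 0.4 | 81.4% | 82.8% | 1.02 |
| | 0.6 | 80.9% | 83.2% | 1.05 |
| | 0.8 | 80.8% | 84.3% | 1.08 |
| 41% vs 54% | 0 | 54.2% | 54.2% | about 1 |
| | 0.4 | 54.5% | 55.6% | 1.04 |
| | 0.6 | 53.7% | 56.4% | 1.10 |
| | 0.8 | 54.8% | 59.9% | 1.15 |

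- At slope 0.2 the variance ratio was 1.00 to 1.01 and the power gain about 1 point.
- A separate run of 2,000 trials per cell at 41% vs 54% and slope 0.8 gave 51% and 58%. That run is the source of the upper limit of 7 points; the table above gives 5.
- At 8.6% vs 21.2% the adjusted test gains 0.7 points even at slope 0. The covariate carries no information there, so up to about a point of the gain in that block reflects the form of the test.
- The variance reduction is 1 − 1/ratio. At slope 0.8 that is 1 − 1/1.08 = 7.4% and 1 − 1/1.15 = 13.0%.
- At 8.6% vs 21.2%, ratios of 1.02 to 1.08 are worth 250 × 0.02 = 5 to 250 × 0.08 = 20 participants.
- With no treatment effect, type I error was 4.7% to 5.1% adjusted and 4.6% to 5.3% unadjusted.

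**The case against.** The strongest reply is that nothing here is wrong. A chi-square in a two-arm randomised trial controls type I error, and chance imbalance is not bias. That stands in full.

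The plan also does not ignore baseline information. Exploratory analyses names baseline dependence, sex and CPD as covariates for the Aim 1 and 2 models. That stands too, although an exploratory set that mixes in post-randomisation variables is no substitute for a pre-specified baseline-adjusted test.

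Next, the documents do not show that FTND or CPD predicts quitting to any stated degree. Section C, Justification & Feasibility, reports that in one study attentional bias was "a better predictor of smoking cessation outcome than traditional measures of dependence". That ranks dependence below attentional bias, gives no strength, and is silent on CPD. A reader might infer from it that the proposed covariates are known strong predictors, but the text does not support that. The gain is therefore conditional, and near zero if the slope is 0.2 or less.

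A risk difference with a confidence interval could also be taken straight from the 2x2 table, so the missing estimate alone does not require adjustment. Finally, the standing of abstinence is ambiguous. Smoking cessation rates are listed with the Exploratory Aims and abstinence is absent from the Aim 2 hypothesis, yet it is analysed and powered under Aim 2. All of this limits how much weight the point can bear. None of it is a reason to prefer the unadjusted test, since adjustment costs almost no precision when the covariates prove uninformative.

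**Conclusion.** The point holds as a modest efficiency and reporting improvement. The only abstinence test named outside the exploratory section leaves available baseline data and the stratification factor unused and gives no effect estimate, and the exploratory versions are unsuitable for estimating the effect on abstinence.

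The size is about 0 to 4 power points at 8.6% vs 21.2% and about 0 to 7 at 41% vs 54%, with variance lower by about 0 to 8% and 0 to 13%. This assumes 1:1 allocation and a slope of 0 to 0.8 per SD for a single baseline score. The documents anchor neither the slope nor any R².

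Two stronger readings are tempting. One is that the chi-square is an error or biases the comparison; it does not. The other is that adjustment would rescue the abstinence comparison. It would not: at the plan's own reference rates power starts near 54% and reaches only about 55% to 60% in the larger simulation (slopes 0.4 to 0.8), so that gap remains.

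**What to change.** In the Aim 2 analysis text, pre-specify for abstinence:

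- logistic regression on arm, baseline FTND, baseline CPD and gender, with missing participants counted as smoking;
- the standardised risk difference (ABM minus sham) with its 95% CI, and its test as the test of abstinence;
- the 2x2 chi-square as a sensitivity analysis;
- a statement that post-randomisation variables (sessions completed, accuracy, CPD at later sessions) do not enter this model.

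The cost is a few lines of analysis wording. No new data, visits or participants are needed.
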